To demonstrate that the home monitoring of a PRN regimen with the CRYSTALSIGHT telemonitoring system is non-inferior to the Amsler grid¹ in detecting recurrence of wet AMD based on central retinal thickness (CRT) increase of at least 50 microns or a loss of best-corrected visual acuity (BCVA) of 5 letters or more.

Detection of using visual field test gaze tracking results in earlier detection of AMD/DME associated with (CNV), as reflected by better visual acuity compared with standard care. Outcome of this trial is to determine the sensitivity and specificity of CRYSTALSIGHT with reactivation subtle neovascular age-related macular degeneration that was detected by the regular use of a home monitoring device based on gaze-based preferential hyperacuity visual field testing.

An important predictor of the benefit of treatment with anti-vascular endothelial growth factor (VEGF) agents is visual acuity at the time of CNV treatment.

Secondary Objectives

1. Correlate CRYSTALSIGHT scores with BCVA and OCT findings.
2. Identify diagnostic performance of CRYSTALSIGHT (ROC, AUC).
3. Develop risk scoring algorithms for wet AMD recurrence.

Background work

For patients who have lost vision in one eye due to wet age-related macular degeneration (wAMD), preservation of functional visual acuity in the other eye is of paramount importance. However, clinical experience and research have shown that these and other high-risk patients often fail to use the Amsler grid between clinic visits to detect the earliest signs of neovascularization in their good eye.

Normal human vision consists of a series of rapid eye movements called saccades that abruptly change the fixation point depending on the area of the person's eye. OCCUTRACK's CRYSTALSIGHT device tracks these eye movements with generated

OCCUTRACK

patterns on the screen, a visual assessment of affected and unaffected eyes is achieved without expensive optics and at home on any tablet or laptop computer.

CRYSTALSIGHT is a home-based gaze-tracking readily available for home hyperacuity monitoring for these and other high-risk eyes with diagnosed wet-AMD.

The Device

[figure not shown]

Figure 1 CRYSTALSIGHT device being used in a home-based setting.

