A single large discrete target is displayed filling the entirety of the screen and shrinks to 10pixels for 5 seconds. The target is presented twice. The user under test's fixation radius is scored as a Circular-Error Probable (CEP) size. The smaller the CEP radius, the better the test result.	A set of 13 discrete targets are displayed randomly and twice repeatedly on fixed coordinates for a preset duration of 1 second (adjustable) on the screen for the user under test. Targets are presented in a pseudo-randomly to avoid bias in gaze point detection. An area-of-effect radius is scored if the user's gaze intersects with the presented target.	A set of 13 discrete targets that increases in radius at 10 pixels/second are displayed randomly on fixed coordinates on the screen for the user under test. Targets are presented in a pseudo-randomly to avoid bias in gaze point detection. The target radius is scored if the user's gaze intersects with the presented target at the presented radius size. The smaller the radius, the better the test result.	Subject under test to pursue a generated target moving in a sinusoidal pattern at a speed of 5cm/s.

OCCUTRACK

Methodology

This study aims to determine whether home-based monitoring using the CRYSTALSIGHT gaze-based Hyperacuity Perimetry system, when added to a PRN treatment regimen, is non-inferior to standard care using the Amsler Grid in detecting recurrence of choroidal neovascularisation (CNV) associated with wet age-related macular degeneration (AMD).

Recurrence is defined by a central retinal thickness (CRT) increase of ≥ 50 microns or a loss of best-corrected visual acuity (BCVA) of ≥ 5 letters.

The study also aims to evaluate whether CRYSTALSIGHT enables earlier detection of CNV progression, as reflected by better VA and CRT values at the time of detection, through biweekly self-tests conducted in an unsupervised home setting.

Study Design

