This is a randomised, open-label, non-inferiority clinical trial comparing two parallel arms: a standard care arm using Amsler Grid home monitoring (PRN), and an intervention arm using the CRYSTALSIGHT gaze-tracking system (PRN+). A total of 220 (Singapore – 60, United Kingdom – 80, United States – 80) participants will be randomised in a 1:1 ratio. Participants in the intervention arm will self-administer biweekly CRYSTALSIGHT tests at home, while those in the control arm will use the Amsler Grid. Both arms will attend monthly clinic visits for standard evaluations, including VA, BCVA, and OCT. Alerts generated by the CRYSTALSIGHT system based on deviation thresholds will trigger early clinic recall for confirmatory imaging and potential re-treatment.

[figure not shown]

Figure 4 Details of the home-use clinical trial study design. The trial objective: show that PRN+ is non-inferior to standard of care PRN with better VA/VF outcomes

Development of CRYSTALSIGHT cutoff scores should have been conducted in the cohort-1 1 study [NCT: NCT06518512] (Analysis). This Phase 2 should be the application of validated cut-off scores. The second aim will be to compare the accuracy of CRYSTALSIGHT and Amsler, and sensitivity and specificity check.

In addition to identifying CRYSTALSIGHT visual risk prediction cut-off scores, detection yields, and diagnostic Performance indicators will also be evaluated. Progression to CNV was

OCCUTRACK

determined by the investigator, based on standardised OCT confirmation. At the clinical trial site, these events were confirmed by gradings conducted by masked, certified independent personnel who did not know the treatment assignment. Events from both arms are graded using a standardised protocol.

[figure not shown]

Figure 5 In Cohort 2, home-based score deviation detected, study coordinator will schedule hospital checkup immediately. If CRYSTALSIGHT correctly detects wet AMD recurrence confirmed by OCT, subject exits the study.

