This study will use the CRYSTALSIGHT system in an unsupervised home setting. Participants will perform biweekly self-monitoring with the CRYSTALSIGHT device. The threshold algorithm will be implemented and validated with subjects. Threshold information from Cohort 1 will thus be incorporated into the Cohort 2 intervention measures. Figure 5 illustrates the function of the CRYSTALSIGHT score as the basis for an intervention measure: an earlier-than-expected clinic visit should be scheduled immediately for clinic vision testing and urgent anti-VEGF administration.

Pro Re Nata (PRN): Standard treatment (control arm)

Participants randomized to the standard treatment arm received specific instructions from investigators for self-monitoring of vision at home to detect progression of AMD. Aids such as the Amsler grid. This group is referred to below as the standard treatment group. If participants experienced symptoms, they were instructed to call their clinical centre immediately and schedule an appointment within 72 hours.

PRN+: Home monitoring device (device arm)

In addition to the same standard of care instructions, participants will receive a CRYSTALSIGHT home monitoring device with instructions for installation and use. This arm is referred to below as the device arm. In cases where baseline measurements could not be obtained due to a pre-existing visual field defect in at least one study eye, participants returned the device and continued monitoring with standard treatment only but were still included in the final analyzes in the intent-to-treat (ITT) cohort as part of the device arm.

Participants were encouraged to use the device twice a week, and results were automatically transmitted via internet cloud to a Occutrack's data monitoring center. If testing of the device indicated a change from baseline measurements, an alert was sent from the monitoring center to the participant's clinical center, prompting staff to schedule an appointment with the study ophthalmologist within 72 hours.

This study is an open-label, randomized study designed to evaluate the safety and efficacy of the CRYSTALSIGHT device when used by patients in their own homes. The study will

OCCUTRACK

recruit a group of patients who meet certain eligibility criteria and provide them with the CRYSTALSIGHT device for use at home.

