5. Subjects undergoing treatment for Wet-AMD without any signs and symptoms of recurrence of active AMD (AMD recurrence: choroidal neovascularisation,

OCCUTRACK

intraretinal or subretinal fluid is present) with OCT lesion fluid volume more than 2 mm² or ILM height more than 300µm.

6. Ability to comply with the study protocol, in the investigator's judgment.
7. Subjects must be able to understand and provide informed consent. A signed informed consent form must be provided before any study assessments.

Exclusion criteria

1. Unable to understand verbal spoken instructions and demonstrate device functionality and implementation.
2. Unable to turn on and connect the CRYSTALSIGHT device to a computer independently.
3. Any ocular surgery in the previous 3 months, or vitrectomy in the previous 12 months
4. Any history of macular pathology unrelated to AMD affecting vision or contributing to the presence of intraretinal or subretinal fluid in the study eye
5. Any concurrent intraocular condition in the study eye that, in the opinion of the investigator, could either reduce the potential for visual improvement or require medical or surgical intervention during the study
6. Any prior or concomitant treatment for CNV or vitreomacular-interface abnormalities in the study eye.
7. History of idiopathic or autoimmune-associated uveitis in either eye
8. Active ocular inflammation or suspected or active ocular or periocular infection in either eye.

Study population: patients with recurrent vision problems diagnosed with active Wet-AMD at TTSH eye clinics.

Pre-specified clinical outcome: The prespecified adverse clinical outcome used in this study will be the **recurrence of Active Wet AMD**, which will be identified by an increase in central retinal thickness (CRT) of at least 50 microns or a loss of best-corrected VA of 5 letters or more.

Training

To prepare for home use of the CRYSTALSIGHT device, the following processes are performed in the clinic:

- The examining physician or study coordinator will unpack a CRYSTALSIGHT training unit for the patient to help the patient understand the device and ensure that the home user understands the device, its purpose, and how it works. Instructions on how to set it up at home include connecting the device to a laptop with an Internet connection.

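### The masked grading confirms an OCT-based progression to CNV, which is not tied to the CRT/BCVA recurrence that the trial sets out to detect

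*Protocol*

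**What the plan says.** **The event that is called and graded (Study Design).** The text runs "detection yields, and diagnostic Performance indicators will also be evaluated. Progression to CNV was" and, after a page break, "determined by the investigator, based on standardised OCT confirmation". It adds that "these events were confirmed by gradings conducted by masked, certified independent personnel who did not know the treatment assignment". Events in both arms are said to be graded to a standardised protocol, which is not shown. This is the only description of masked grading in the document.

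**The event that the trial is meant to detect.** The Primary Objective is about "detecting recurrence of wet AMD based on central retinal thickness (CRT) increase of at least 50 microns", or a BCVA loss of 5 letters or more. Methodology states "Recurrence is defined by a central retinal thickness (CRT) increase of ≥ 50 microns", with the same BCVA alternative. The pre-specified clinical outcome under Eligibility is the same event, "which will be identified by an increase in central retinal thickness (CRT) of at least 50 microns or a loss of best-corrected VA"; its letter threshold is again 5.

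**The reference for a correct home test (Sample size calculation).** A result counts as correct when it agrees with the OCT scan. Each participant's accuracy is the number of correct results divided by the number of clinic visits. No CRT or BCVA threshold is given, and neither the graded event nor the recurrence definition is mentioned.

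**When BCVA is measured.** Study Design lists BCVA among the monthly evaluations in both arms. The Study Schedule Table marks it optional at all 12 visits, baseline included.

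**The concern.** Three sections name the event to be detected, the event to be adjudicated and the standard for a correct test, and they do so in three different ways. Only the first carries thresholds. The trial is open-label, and the masked grading is the only safeguard it describes against biased event calls. If that grading is not directed at the defined event, the safeguard does not clearly cover the outcome in the primary objective.

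The definition also has two limbs joined by *or*. An investigator or grader working from OCT can judge the CRT limb but not the BCVA limb. A visit at which a participant has lost 5 letters without a 50-micron thickening is a recurrence by definition, yet it could be recorded as no recurrence. The home test at that visit would then be scored the wrong way round. Two sites reading the same protocol could classify the same visit differently.

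**Working it through.** The point is about definitions, so the main check is a comparison of the sections.

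| Section | Name of the event | Basis | Thresholds |
|---|---|---|---|
| Primary Objective | Recurrence of wet AMD | CRT or BCVA | 50 microns; 5 letters |
| Methodology | Recurrence | CRT or BCVA | 50 microns; 5 letters |
| Pre-specified clinical outcome | Recurrence of active wet AMD | CRT or BCVA | 50 microns; 5 letters |
| Study Design (call and masked grading) | Progression to CNV | OCT | none |
| Sample size calculation (correct result) | Agreement with OCT | OCT | none |

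**Example visits** (illustrative values):

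1. *CRT up 20 microns, BCVA down 5 letters.* This is a recurrence by definition, through the BCVA limb. An OCT-only call has nothing to register, so the visit can be recorded as no recurrence. A positive home test would then be scored wrong and a negative one right, the reverse of what the definition implies.
2. *CRT up 60 microns, no BCVA loss.* This is a recurrence by definition. Whether it is progression to CNV is left to the reader of the scan, because no threshold is stated.
3. *BCVA not measured at the visit*, as the schedule allows. The BCVA limb cannot be evaluated at all, and the protocol does not say how such a visit is classified.

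**The plan's own figure.** For the global study the inputs are SD 0.21, margin 0.09, one-sided 0.025, power 0.8 and true difference 0. Per group, n = 2 × (1.960 + 0.842)² × 0.21² / 0.09² = 85.5, rounded up to 86, or 172 in total. Allowing for 21% dropout, 172 / 0.79 = 218, against 220 stated, so the figure reproduces. (For Singapore the same formula gives 56 against 52 stated, which is a separate matter.) Correcting the event wording changes none of these inputs.

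**Scale of a re-scored visit.** With the scheduled 12 visits, changing the score of one visit moves that participant's accuracy by 1/12 = 0.083. The step is larger for anyone who leaves early, for example 1/6 = 0.167 after six visits. The share *f* of participants with such a visit is not in the protocol. Assume one re-scored visit each over 12 visits, all in the same direction, in one arm only. The difference between arms then moves by *f* × 0.083:

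- *f* = 5%: 0.004
- *f* = 10%: 0.008
- *f* = 20%: 0.017

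The margin is 0.09. Re-scoring in both arms, or in both directions, would partly cancel.

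**The case against.** The strongest reply is that progression to CNV is just loose wording for recurrence. Methodology speaks of recurrence of CNV and defines recurrence in the next sentence; it then uses CNV progression in the same context. The Figure 5 and Figure 6 captions both speak of wet AMD recurrence confirmed by OCT. The standardised grading protocol is not shown and may already apply the thresholds. Much of this stands: the intended event is probably recurrence. It does not close the gap, because no section ties the grading or the accuracy reference to the CRT and BCVA thresholds, and the captions again rest on OCT alone.

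Two stronger readings are tempting, and the protocol does not support either.

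- *A reader might infer that every home test is scored against the graded event, so that grading errors pull the arms together and make non-inferiority easier to declare by a calculable amount.* The Sample size calculation names the OCT scan as the reference, not the graded event. The graders confirm events already called, not every visit. The rate of disagreement is not given. The dilution argument also needs errors unrelated to the home test, which is doubtful when thickening or vision loss may itself drive the test result.
- *A reader might infer that the graded event is impossible here, because treated wet AMD eyes already have CNV.* Inclusion criterion 5 and the word recurrence point that way, but exclusion criterion 6 bars study eyes with prior or concomitant CNV treatment. Those two criteria conflict and must be reconciled separately. Until then, the lesion status of study eyes at entry is not settled by the text.

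**Conclusion.** The point holds as an inconsistency in the current text and should be fixed. The adjudicated event and the accuracy reference are not linked to the defined recurrence, and an OCT-only call cannot capture a recurrence that meets only the BCVA criterion. This rests on the wording alone, not on any assumed error rate.

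The effect on the trial's result cannot be quantified from the protocol, because it gives neither the frequency of BCVA-only recurrences nor the share of visits with BCVA measured. The range under working is illustrative. It suggests a modest shift in the arm difference, with no predictable direction, and supports no statement about the type I error rate. What is certain is that the protocol leaves open which visits count as true recurrences.

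**What to change.** 1. In Study Design, replace progression to CNV with recurrence as defined in Methodology.
2. Have the masked graders apply the 50-micron CRT criterion to the events they already grade. Masked CRT grading at every visit is not needed for this.
3. Apply the 5-letter criterion from the BCVA recorded at the visit, and state that OCT grading does not cover it. Reconcile this with the schedule, where BCVA is optional at every visit although Study Design lists it as a monthly evaluation. Say how a visit without BCVA is classified.
4. In the Sample size calculation, use the same event as the reference for a correct result in both arms.

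Items 1, 2 and 4 are changes to protocol and grading-form wording, with no extra participants or scans, and are best made before grading begins. Item 3 may cost more than wording, depending on how the BCVA entries are reconciled. No stated sample size changes.

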The Cohort 2 study typically several phases, including a screening phase to identify eligible patients who could be recruited patients exiting the anti-VEGF injection clinic. The phases are:

- **Training:** a training phase for the device to ensure that patients know how to use the device properly, a testing phase in which patients use the device to monitor their vision condition using the CRYSTALSIGHT device over a period of time until the device detects deterioration in vision and meets the criteria for deterioration established by the Cohort 1 results, and a follow-up phase to assess results and obtain feedback from patients.
- **Monitoring:** During the study, patients will be asked to follow the specific protocols and guidelines for use of the CRYSTALSIGHT device, such as completing the bi-weekly regular testing. Patients will also be asked to report or provide feedback on any adverse events or problems encountered while using the device.
- **Intervention:** Should the CRYSTALSIGHT device determine that a threshold for vision deterioration has been reached (delta deviation of 10 points from the nominal baseline), the patient/participant will receive a notification from the prescribing physician and the electronic alert system via email to the subject's personal mobile device instructing them to schedule an appointment for confirmation OCT -A that the subject's wet AMD has recurred, see Figure 6 below.

[figure not shown]

Figure 6 True-False confusion matrix of cohort-2 will require OCT confirmation of wet AMD disease recurrence that was detected by CRYSTALSIGHT.

This cohort 2 intervention study is designed to collect data on the safety and efficacy of the device, including information on the accuracy, reliability, and ease of use of the device. The study may also examine the impact of the device on patient outcomes, such as changes in visual status or quality of life.

Once the study is complete, the data will be analyzed to determine if the device is safe and effective for home use. If the results are positive, the device can be submitted to the FDA for approval and made available to patients who need it.

OCCUTRACK

Cohort-2 study relationship to the cohort-1

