For participants in the CRYSTALSIGHT group, each participant will have a testing result by CRYSTALSIGHT and by OCT every 4 weeks or less if the positive result triggers a clinical visit. The result is considered correct if it is consistent with the findings of the OCT scan. During the one-year study period, the total number of correct results generated by CRYSTALSIGHT will be counted and the accuracy for these participants will be calculated as number of correct results divided by the total number of clinical visit. For participants in the Amsler Grid group, the accuracy for each participant will also be calculated.

According to literature, the accuracy of Amsler Grid in detecting disease activity was about 80%, we will assume that CRYSTALSIGHT has the same accuracy. For the Singapore population, we will also assume that standard deviation of the accuracy to be 0.12 and setting the maximum allowable difference in accuracy (non-inferiority margin) between the two groups to be 0.09, with one-sided type 1 error of 0.025 and a power of 0.8, a total of 52 participants will be required (26 per group). Considering of 15% attrition rate, a total of 60 participants will be required.

For global study, we assume a higher standard deviation of the accuracy to be 0.21 and a dropout rate of 21%, a total of 220 participants will be required (110 per group).

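### Masked grading is described only for events the open-label investigator has called, and the OCT reference for accuracy is neither tied to the recurrence definition nor named consistently at alert visits

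*Protocol*

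**What the plan says.** **Who determines events.** The Protocol's Study Design section states: "This is a randomised, open-label, non-inferiority clinical trial comparing two parallel arms". In the same section, progression to CNV is "determined by the investigator, based on standardised OCT confirmation". It continues that "these events were confirmed by gradings conducted by masked, certified independent personnel who did not know the treatment assignment", and that "Events from both arms are graded using a standardised protocol". It does not mention grading of visits at which no event was called.

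**Who sees the device result.** Under The Device, the principal investigator compares flagged results with the patient's baseline. Under PRN+ (device arm), alerts go to the participant's clinical centre. Under Results and reporting, the principal investigator and study coordinator analyse the home-test results.

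**What counts as recurrence.** The Primary Objective, Methodology and Pre-specified clinical outcome all use a CRT rise of at least 50 microns or a BCVA loss of at least 5 letters.

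**What the accuracy measure uses.** The Sample size calculation says: "The result is considered correct if it is consistent with the findings of the OCT scan". Each participant's accuracy is the number of correct results divided by the number of clinic visits. No threshold for the OCT finding is given there.

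**Imaging after an alert.** The Intervention item in Study Design tells the participant to "schedule an appointment for confirmation OCT -A". The captions of Figures 5 and 6 and the Sample size calculation name OCT for these visits. The Study Schedule Table lists OCT at every visit, does not list OCT-A, and marks BCVA as optional throughout.

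**The concern.** Accuracy is only as sound as the reference it is scored against. That reference should be fixed without knowledge of the arm or the home-test result, and in the same way at every visit. Three features of the text leave room for it not to be:

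- The person who first calls an event can know both the arm and the alert, and masked review is described only after that call.
- The accuracy rule refers to OCT findings in general, although a numeric definition is available.
- One sentence attaches a different imaging method to device alerts alone.

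An investigator who knows of an alert may look more closely or call an event more readily at that visit. If that call is the scored reference, the device's apparent accuracy can rise without the device being any better. In a non-inferiority trial sized on a 0.09 difference in accuracy, even a small net shift matters.

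**Working it through.** **1. What masked grading can correct, as described**

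| Investigator's call | True state | Described as reaching masked graders? | Consequence |
|---|---|---|---|
| Event | No recurrence | Yes | False call can be removed |
| Event | Recurrence | Yes | Confirmed |
| No event | No recurrence | Not described | None |
| No event | Recurrence | Not described | Missed recurrence is not recovered |

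In the last row, if the investigator's call is taken as the OCT finding, a negative home test is scored correct and a positive one incorrect, and both scores are wrong. The protocol does not say whether that call or the 50-micron rule supplies the OCT finding. This gap is part of the problem.

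**2. Imaging at an alert visit, side by side**

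- Intervention item: OCT-A.
- Figure 5 caption: recurrence confirmed by OCT.
- Figure 6 caption: the confusion matrix requires OCT confirmation.
- Sample size calculation: management after recall follows the OCT scan. OCT is done every 4 weeks, or sooner when a positive result triggers a visit, and correctness is scored against OCT.
- Recurrence definition: CRT or BCVA, with no OCT-A criterion.

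OCT-A therefore appears once and conflicts with the other statements. If that sentence governed scoring, the reference would depend on the device result.

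**3. The plan's own sample size**

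Inputs from the Sample size calculation: equal accuracy in both arms, margin 0.09, SD 0.21 (global), one-sided alpha 0.025, power 0.80, dropout 21%.

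- n per arm = 2 × 0.21² × (1.960 + 0.842)² / 0.09² ≈ 85.5, so 86 per arm and 172 in total.
- 172 / (1 − 0.21) = 217.7, so 218. The protocol states 220, and a t-based version gives 221. The global figure reproduces.

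**4. Illustration of sensitivity to a shift**

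The shift b is an assumption; the documents give no verification-error rate.

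- SE = 0.21 × √(2/86) ≈ 0.032.
- Type I error at the margin, with b favouring the device: 1 − Φ(1.960 − b/SE).
- Power at true equality, with b against the device: Φ((0.09 − b)/SE − 1.960).

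| Net shift b | Type I error, shift favours device | Power, shift against device |
|---|---|---|
| 0 | 2.5% | 80% |
| 0.01 | 5.0% | 70% |
| 0.02 | 9.1% | 59% |
| 0.03 | 15.3% | 47% |

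**The case against.** The case on the other side has four parts.

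**The scored reference is already OCT.** The Sample size calculation covers triggered visits expressly, both figure captions name OCT, and both arms have monthly OCT whatever the home test shows. This stands. A reader might infer from the Intervention item that alert visits are verified by OCT-A and all others by OCT. The documents do not support that as a settled rule; they support only a contradiction to be reconciled.

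**Silence is not exclusion.** The text describes masked confirmation of events and is silent on non-events. The selection of scans could be set in the grading protocol or in an SAP that is not shown. A reader might infer that visits called negative are never read blind, but the documents do not say so. What stands is that the only route described to masked grading runs through the investigator's call.

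**The numeric definition limits judgement.** It would do so if the accuracy rule used it. That rule refers only to OCT findings, and the adjudication sentences concern progression to CNV, so the protection is available but not applied.

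**The size is unknown.** This also stands. It is tempting to suppose that 20% of device results are OCT-negative alerts, that 10 to 30% of these are turned positive, and so to claim a gain of 2 to 6 points (0.20 × 0.10 to 0.20 × 0.30). That estimate is not supported. At the assumed 80% accuracy it makes every error a false alert, gives masked review no effect on exactly the calls it would see, and assumes no corresponding shift at the control arm's symptom-triggered visits.

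**Conclusion.** The point holds in a limited form. The reference for accuracy is not fixed independently of a person who can know the arm and the alert. The described masked review works in one direction only. The scoring rule is not linked to the protocol's own recurrence definition, and the imaging at alert visits is stated inconsistently.

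That the investigator may be influenced, and that graders see only called events, are fair readings of an open-label design and of the adjudication sentences; neither is stated outright. Monthly OCT in both arms limits the possible harm. Neither the direction nor the size of any bias can be established from the documents. The range of about 5 to 15% for type I error is conditional on an assumed net shift of 1 to 3 points favouring the device, 86 evaluable per arm, SD 0.21 and a normal approximation. It shows how little shift is needed to matter, not how much is expected. The sample size does not change.

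**What to change.** 1. For the accuracy endpoint, derive the reference at every visit, scheduled or triggered, in both arms from OCT-measured CRT change against the 50-micron threshold. Use recorded values and not the investigator's call.
2. Apply the 5-letter rule on a basis that does not depend on alert status. Because the schedule marks BCVA as optional, state when it enters the scoring so that it is not available more often at alert visits.
3. Reconcile the Intervention item with the Figure 5 and 6 captions and the Sample size calculation, so that the same OCT is the scored reference at all visits. Any OCT-A is supportive only for scoring. This concerns the endpoint and leaves clinical imaging decisions to the sponsor and investigators.
4. Keep masked grading as a check, and state which visits the graders read. Including a sample of investigator-negative visits from both arms would show whether recurrences are being missed.

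Items 1 to 3 need revised endpoint wording and one derived variable. CRT must be captured as a data field at each OCT, since the schedule lists the scan but not the measurement. Some events the investigator called may no longer count as correct alerts. The optional sample in item 4 adds some reading work. No additional scheduled OCT is needed.
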